11.3 Guidelines for Evaluation of Measurable Disease

11.31 Measurement Methods:

- All measurements should be recorded in metric notation (i.e., decimal fractions of centimeters) using a ruler or calipers.
- The same method of assessment and the same technique must be used to characterize each identified and reported lesion at baseline and during follow-up. For patients having only lesions measuring at least 1 cm to less than 2 cm must use CT imaging for both pre- and post-treatment tumor assessments.
- Imaging-based evaluation is preferred to evaluation by clinical examination when both methods have been used at the same evaluation to assess the antitumor effect of a treatment.

11.32 Acceptable Modalities for Measurable Disease:

- Conventional CT and MRI: This guideline has defined measurability of lesions on CT scan based on the assumption that CT slice thickness is 5 mm or less. If CT scans have slice thickness greater than 5 mm, the minimum size for a measurable lesion should be twice the slice thickness.
- As with CT, if an MRI is performed, the technical specifications of the scanning sequences used should be optimized for the evaluation of the type and site of disease. The lesions should be measured on the same pulse sequence. Ideally, the same type of scanner should be used and the image acquisition protocol should be followed as closely as possible to prior scans. Body scans should be performed with breath-hold scanning techniques, if possible.
- PET-CT: If the site can document that the CT performed as part of a PET-CT is of identical diagnostic quality to a diagnostic CT (with IV and oral contrast), then the CT portion of the PET-CT can be used for RECIST measurements and can be used interchangeably with conventional CT in accurately measuring cancer lesions over time.
- FDG-PET: FDG-PET scanning is allowed to complement CT scanning in assessment of progressive disease [PD] and particularly possible 'new' disease. A 'positive' FDG-PET scanned lesion is defined as one which is FDG avid with an uptake greater than twice that of the surrounding tissue on the attenuation corrected image; otherwise, an FDG-PET scanned lesion is

considered ‘negative.’ New lesions on the basis of FDG-PET imaging can be identified according to the following algorithm:

- a. Negative FDG-PET at baseline with a positive FDG-PET at follow-up is a sign of PD based on a new lesion.
- b. No FDG-PET at baseline and a positive FDG-PET at follow-up:
 - i. If the positive FDG-PET at follow-up corresponds to a new site of disease confirmed by CT, this is PD.
 - ii. If the positive FDG-PET at follow-up is not confirmed as a new site of disease on CT at the same evaluation, additional follow-up CT scans (i.e., additional follow-up scans at least 4 weeks later) are needed to determine if there is truly progression occurring at that site. In this situation, the date of PD will be the date of the initial abnormal PDG-PET scan.
 - iii. If the positive FDG-PET at follow-up corresponds to a pre-existing site of disease on CT that is not progressing on the basis of the anatomic images, it is not classified as PD.

11.33 Measurement at Follow-up Evaluation:

- A subsequent scan must be obtained ≥ 4 weeks following initial documentation of an objective status of either complete response (CR) or partial response (PR).
- In the case of stable disease (SD), follow-up measurements must have met the SD criteria at least once after study entry at a minimum interval of 4 weeks (see Section 11.44).
- The cytological confirmation of the neoplastic origin of any effusion that appears or worsens during treatment when the measurable tumor has met criteria for response or stable disease is mandatory to differentiate between response or stable disease (an effusion may be a side effect of the treatment) and progressive disease.
- Cytologic and histologic techniques can be used to differentiate between PR and CR in rare cases (e.g., residual lesions in tumor types such as germ cell tumors, where known residual benign tumors can remain.)

11.4 Measurement of Effect

11.41 Target Lesions & Target Lymph Nodes

- Measurable lesions (as defined in Section 11.21) up to a maximum of 5 lesions, representative of all involved organs, should be identified as “Target Lesions” and recorded and measured at baseline. These lesions can be non-nodal or nodal (as defined in 11.21), where no more than 2 lesions are from the same organ and no more than 2 malignant nodal lesions are selected.

Note: If fewer than 5 target lesions and target lymph nodes are identified (as there often will be), there is no reason to perform additional studies beyond those specified in the protocol to discover new lesions.

- Target lesions and target lymph nodes should be selected on the basis of their size, be representative of all involved sites of disease, but in addition should be those that lend themselves to reproducible repeated measurements. It may be the case that, on occasion, the largest lesion (or malignant lymph node) does not lend itself to reproducible measurements in which circumstance the next largest lesion (or malignant lymph node) which can be measured reproducibly should be selected.
- Baseline Sum of Dimensions (BSD): A sum of the longest diameter for all target lesions plus the sum of the short axis of all the target lymph nodes will be calculated and reported as the baseline sum of dimensions (BSD). The BSD will be used as reference to further characterize any objective tumor response in the measurable dimension of the disease.
- Post-Baseline Sum of the Dimensions (PBSD): A sum of the longest diameter for all target lesions plus the sum of the short axis of all the target lymph nodes will be calculated and reported as the post-baseline sum of dimensions (PBSD). If the radiologist is able to provide an actual measure for the target lesion (or target lymph node), that should be recorded, even if it is below 0.5 cm. If the target lesion (or target lymph node) is believed to be present and is faintly seen but too small to measure, a default value of 0.5 cm should be assigned. If it is the opinion of the radiologist that the target lesion or target lymph node has likely disappeared, the measurement should be recorded as 0 cm.
- The minimum sum of the dimensions (MSD) is the minimum of the BSD and the PBSD.

11.42 Non-Target Lesions & Non-Target Lymph Nodes

Non-measurable sites of disease (Section 11.22) are classified as non-target lesions or non-target lymph nodes and should also be recorded at baseline. These lesions and lymph nodes should be followed in accord with 11.433.

11.43 Response Criteria

- 11.431 All target lesions and target lymph nodes followed by CT/MRI/PET-CT/Chest X-ray/physical examination must be measured on re-evaluation at evaluation times specified in Section 11.1. Specifically, a change in objective status to either a PR or CR cannot be done without re-measuring target lesions and target lymph nodes.

Note: Non-target lesions and non-target lymph nodes should be

evaluated at each assessment, especially in the case of first response or confirmation of response. In selected circumstances, certain non-target organs may be evaluated less frequently. For example, bone scans may need to be repeated only when complete response is identified in target disease or when progression in bone is suspected.

11.432 Evaluation of Target Lesions

- Complete Response (CR): All of the following must be true:
 - a. Disappearance of all target lesions.
 - b. Each target lymph node must have reduction in short axis to <1.0 cm.
- Partial Response (PR): At least a 30% decrease in PBSD (sum of the longest diameter for all target lesions plus the sum of the short axis of all the target lymph nodes at current evaluation) taking as reference the BSD (*see* Section 11.41).
- Progression (PD): At least one of the following must be true:
 - a. At least one new malignant lesion, which also includes any lymph node that was normal at baseline (< 1.0 cm short axis) and increased to ≥ 1.0 cm short axis during follow-up.
 - b. At least a 20% increase in PBSD (sum of the longest diameter for all target lesions plus the sum of the short axis of all the target lymph nodes at current evaluation) taking as reference the MSD (Section 11.41). In addition, the PBSD must also demonstrate an absolute increase of at least 0.5 cm from the MSD.
 - c. See Section 11.32 for details in regards to the requirements for PD via FDG-PET imaging.
- Stable Disease (SD): Neither sufficient shrinkage to qualify for PR, nor sufficient increase to qualify for PD taking as reference the MSD.

11.433 Evaluation of Non-Target Lesions & Non-target Lymph Nodes

- Complete Response (CR): All of the following must be true:
 - a. Disappearance of all non-target lesions.
 - b. Each non-target lymph node must have a reduction in short axis to <1.0 cm.
- Non-CR/Non-PD: Persistence of one or more non-target lesions or non-target lymph nodes.
- Progression (PD): At least one of the following must be true:
 - a. At least one new malignant lesion, which also includes any lymph node that was normal at baseline (< 1.0 cm short axis) and increased to \geq 1.0 cm short axis during follow-up.
 - b. Unequivocal progression of existing non-target lesions and non-target lymph nodes. (NOTE: Unequivocal progression should not normally trump target lesion and target lymph node status. It must be representative of overall disease status change.)
 - c. See Section 11.32 for details in regards to the requirements for PD via FDG-PET imaging.

11.44 Overall Objective Status

The overall objective status for an evaluation is determined by combining the patient's status on target lesions, target lymph nodes, non-target lesions, non-target lymph nodes, and new disease as defined in the following table:

Target Lesions & Target Lymph Nodes	Non-Target Lesions & Non-Target Lymph Nodes	New Sites of Disease	Overall Objective Status
CR	CR	No	CR
CR	Non-CR/Non-PD	No	PR
PR	CR Non-CR/Non-PD	No	PR
CR/PR	Not All Evaluated*	No	PR**
SD	CR Non-CR/Non-PD Not All Evaluated*	No	SD
Not all Evaluated	CR Non-CR/Non-PD Not All Evaluated*	No	Not Evaluated (NE)
PD	Unequivocal PD CR Non-CR/Non-PD Not All Evaluated*	Yes or No	PD
CR/PR/SD/PD/Not all Evaluated	Unequivocal PD	Yes or No	PD
CR/PR/SD/PD/Not all Evaluated	CR Non-CR/Non-PD Not All Evaluated*	Yes	PD

*See Section 11.431

** NOTE: This study uses the protocol RECIST v1.1 template dated 2/16/2011. For data collection and analysis purposes the objective status changed from SD to PR in the ACCRU protocol RECIST v1.1 template as of 2/16/2011 and to match RECIST v1.1 requirements.

Note: For those patients who have initial PD in the first 12 weeks post-registration, a confirmation scan will be required 4 weeks later to confirm PD. See Section 13.7 for further details. If progression is confirmed then the date of disease progression will be the first date the patient met the criteria for progression based on standard RECIST 1.1 criteria.

11.45 Symptomatic Deterioration: Patients with global deterioration of health status requiring discontinuation of treatment without objective evidence of disease progression at that time, and not either related to study treatment or other medical conditions, should be reported as PD due to “symptomatic deterioration.” Every effort should be made to document the objective progression even after discontinuation of treatment due to symptomatic deterioration. A patient is classified as having PD due to “symptomatic deterioration” if any of the following occur that are not either related to study treatment or other medical conditions:

- Weight loss >10% of body weight.
- Worsening of tumor-related symptoms.
- Decline in performance status of >1 level on ECOG scale.

12.0 Descriptive Factors

- 12.1 Region: North America vs. Europe
- 12.2 Disease TNM stage at diagnosis: I vs. II vs. III vs. 4A vs. 4B vs. 4C
- 12.3 History of lymphocytic thyroiditis: Yes vs. No
- 12.4 Prior systemic VEGFR-active kinase inhibitor therapy: Yes vs. No
- 12.5 Histologic subtype of primary tumor: papillary vs. follicular variant vs. follicular vs. Hurthle or poorly differentiated
- 12.6 Sites of metastatic lesions: none vs. nodal vs. pulmonary vs. bone vs. liver vs. CNS/brain vs. subcutaneous tissue vs. other

13.0 Treatment/Follow-up Decision at Evaluation of Patient

- 13.1 Patients who are CR, PR, or SD will continue treatment per protocol.
- 13.2 Patients who develop PD while receiving therapy or refuse treatment or choose alternative therapy will go to the event-monitoring phase per Section 18.0 and be followed every 180 days for a maximum of 3 years from study registration. (See exceptions in 13.5 and 13.6.)
- 13.3 Patients who go off protocol treatment for reasons other than those listed in Section 13.2 above (e.g., adverse events, other complicating disease) will go to Observation and will follow the test schedule (Section 4.0) every 84 days for a maximum of 3 years from study registration. If they progress or choose alternative therapy while in Observation, they will go to the event-monitoring phase.
- 13.4 OBSERVATION: The study treatment period is 54 weeks (19 cycles). Patients who are receiving clinical benefit (i.e., in CR or PR or SD) and who are tolerating treatment at the end of the study treatment period may continue on therapy for an additional 12 months. After study treatment has been discontinued, they should be observed every 12 weeks until PD or a maximum follow-up of 3 years from study registration. Once the patient has PD during observation, they will be followed in the event-monitoring phase for a maximum follow-up of 3 years from study registration (see Section 18.0). Subsequent treatment is at the discretion of their attending physician. NOTE: If the patient continues for an additional 12 months of treatment beyond the initial 54 weeks, the patient should follow the same test schedule, per protocol, as is done during the initial 54-week period.
- 13.5 Patients who develop PD in the CNS may receive radiotherapy and continue treatment on study after completion of radiotherapy. **NOTE: Both lenvatinib and pembrolizumab should be withheld for a minimum of 3 days prior to radiation and for 3 weeks after radiation.**

13.6 Accumulating evidence indicates a minority of patients treated with immunotherapy may derive clinical benefit despite initial evidence of PD. Patients receiving treatment in this study will be permitted to continue treatment beyond initial PD, if the initial PD happens in the first 12 weeks post-registration (by RECIST 1.1), as long as they meet the following criteria:

- Investigator-assessed clinical benefit (e.g. absence of rapid disease progression and absence of progressive tumor at a critical anatomic site that requires urgent alternative intervention), and
- The patient is tolerating study drug.
- Patient does not continue to progress at 4 week follow-up imaging after PD first noted.

Patients with initial progression will be assessed with clinical judgment as to whether the patient is deriving clinical benefit from treatment and should continue study treatment or discontinue and enter the follow up/survival phase of the study. If progression is confirmed then the date of disease progression will be the first date the patient met the criteria for progression based on the standard RECIST 1.1 criteria.

13.7 A patient is deemed *ineligible* if after registration, it is determined that at the time of registration, the patient did not satisfy each and every eligibility criteria for study entry. The patient may continue treatment off-protocol at the discretion of the physician as long as there are no safety concerns, and the patient was properly registered. The patient will go directly to the event-monitoring phase of the study (or off study, if applicable).

- If the patient received treatment, all data up until the point of confirmation of ineligibility must be submitted. Event monitoring will be required per Section 18.0 of the protocol.
- If the patient never received treatment, on-study material must be submitted. Event monitoring will be required per Section 18.0 of the protocol.

13.8 A patient is deemed a *major violation*, if protocol requirements regarding treatment in cycle 1 of the initial therapy are severely violated that evaluability for primary end point is questionable. All data up until the point of confirmation of a major violation must be submitted. The patient will go directly to the event-monitoring phase of the study. The patient may continue treatment off-protocol at the discretion of the physician as long as there are no safety concerns, and the patient was properly registered. Event monitoring will be required per Section 18.0 of the protocol.

13.9 A patient is deemed a *cancel* if he/she is removed from the study for any reason before any study treatment is given. On-study material and Off-Treatment Form must be submitted. Event monitoring will be required per protocol (Section 18.0).

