16.2 Sample Size/Accrual Rate

16.21 Sample Size: A total of 25 evaluable Cohort 1 and 25 evaluable Cohort 2 patients will be accrued per study design (50 evaluable total), unless one or both cohorts of the study are permanently closed at the stage 1 analysis or undue

toxicity is observed. We anticipate accruing an additional 10 patients (5 Cohort 1, 5 Cohort 2) in order to account for ineligibility, cancellation, major treatment violation, or other reasons. Therefore, maximum accrual is 60 patients for this trial (30 for each Cohort).

16.22 Accrual Time and Study Duration: We expect to accrue about 3 patients per month to this trial. Therefore, the accrual period for this Phase II study is expected to be about 20 months. We anticipate that the study will take approximately 3 years to complete. This allows a 6 month follow-up for the final patient enrolled, along with data entry, data clean-up, and analysis.

16.3 Analysis of Secondary Endpoints for both Cohorts.

This study will assess multiple secondary endpoints, including adverse events, progression-free survival (PFS) and overall survival (OS). All these analyses will be done for each cohort separately. In addition, all primary/secondary data will be summarized by descriptive factors as well (i.e. prior treatment, etc.).

16.31 Adverse Events: All patients that have initiated treatment will be considered evaluable for assessing adverse events. The maximum grade for each type of adverse event will be recorded for each patient, and frequency tables will be reviewed to determine adverse event patterns. Only the grade 2+ adverse events will be assessed, regardless of relationship to the study treatment.

16.32 Progression-Free Survival (PFS): Defined as the time from registration to the first of either death due to any cause or progression. The distribution of PFS will be estimated using the method of Kaplan-Meier.

16.33 Overall Survival: Defined as the time from registration to death due to any cause. The distribution of survival time will be estimated using the method of Kaplan-Meier. Special attention will be paid to any registered patient who dies early (i.e., within 60 days) of initiating their treatment. Circumstances surrounding such early deaths will be classified as being either due to malignant disease, toxicity, other causes, or of unknown reasons.

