2. Submit only if applicable.
3. Complete at each evaluation during Observation (see Section 4.0).
4. Upload a copy of documentation of progression in RAVE on the Supporting Documentation Form.

Follow-up Material(s)

CRF	Event Monitoring Phase ¹			
	At PD	After PD q. 6 mos.	Death	New Primary
Patient Status: Survival and Disease Status Follow-up/Event Monitoring	X	X	X	At each occurrence
Adverse Events: Late	X	X		
Notice of New Primary				X
Consent Withdrawal 
 • Consent Withdrawal: Specimens Only • Consent Withdrawal: Clinical Follow-Up Only • Consent Withdrawal: All Follow-Up 	X ²	X ²	X ²	X ³
Lost to Follow-up	X ²	X ²	X ²	
ACCRU Deviation Form ²	X ²	X ²	X ²	

1. If a patient is still alive 3 years after registration, no further follow-up is required.
2. Submit only if applicable.

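### Progression-free patients who refuse further treatment leave scheduled tumour imaging under Section 13.2, while those who stop for adverse events keep it under Section 13.3

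*Combined protocol and SAP*

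**What the plan says.** Section 13.2 puts three groups on one route: "Patients who develop PD while receiving therapy or refuse treatment or choose alternative therapy will go to the event-monitoring phase per Section 18.0". They are to "be followed every 180 days for a maximum of 3 years from study registration".

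Section 13.3 covers patients who stop for other reasons and gives adverse events as an example. They "will go to Observation and will follow the test schedule (Section 4.0) every 84 days for a maximum of 3 years from study registration". It adds: "If they progress or choose alternative therapy while in Observation, they will go to the event-monitoring phase".

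Section 18.1 lists RECIST Measurements and Supporting Documentation on treatment, at end of treatment and in Observation. The event-monitoring table lists neither. Its status form is "Patient Status: Survival and Disease Status Follow-up/Event Monitoring", and its columns are At PD, "After PD q. 6 mos", Death and New Primary. Section 18.1 also has separate consent-withdrawal forms for specimens, clinical follow-up and all follow-up.

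Section 16.32 defines PFS for every patient: "Defined as the time from registration to the first of either death due to any cause or progression". It gives no censoring rule.

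Section 11.33 makes a scan mandatory at least 4 weeks after a first CR or PR and states no exemption for patients off treatment. Section 16.14 builds confirmation into the Cohort 2 primary endpoint. Section 16.12 does not do so for Cohort 1.

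**The concern.** Two patients with the same disease status are followed differently because of the reason recorded for stopping. One has tumour assessments every 84 days. The other has a contact every 180 days with no imaging form attached. The boundary between the reasons can be soft: note c to the table in Section 8.2 leaves it to the subject and the investigator together to judge whether a Grade 2 toxicity is tolerable. A patient who gives up a daily oral drug over bothersome side effects could plausibly be recorded either way.

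Refusing treatment is not refusing follow-up. The separate withdrawal forms in Section 18.1 already recognise this, but Section 13.2 makes no use of the distinction.

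Two things are at stake. PFS, a secondary endpoint in both cohorts, would rest on different methods of ascertainment within a cohort, and the difference may be related to prognosis. In Cohort 2, a responder who refuses between the first response and the repeat scan could lose the confirmation needed to count as a success.

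**Working it through.** **Step 1. The two routes for a patient without PD who has started no other therapy**

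| | Refuses treatment (13.2) | Stops for an adverse event (13.3) |
|---|---|---|
| Phase | Event monitoring | Observation |
| Interval | 180 days | 84 days |
| RECIST form in that phase (18.1) | Not listed | Listed |
| Scheduled form while alive without PD (18.1) | No column | Each Observation visit |
| Progression counted in PFS (16.32) | Yes | Yes |

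Section 13.2 promises 180-day follow-up, but the only periodic column in the event-monitoring table begins after PD. The two sections do not match for this patient.

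**Step 2. How many patients**

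No refusal rate is given. Assume 5% to 15% of the 30 patients accrued per cohort: 0.05 × 30 = 1.5 and 0.15 × 30 = 4.5.

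**Step 3. Illustrative detection lag for PFS**

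Assume exponential progression times with rate λ = ln 2 / median, and detection at the next scheduled contact on a grid of d days. The mean lag is d/(1 − e^(−λd)) − 1/λ. The longest median used, 18.3 months, is the lenvatinib figure in Section 1.6. The medians of 6 and 12 months are assumptions.

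| Median PFS | d = 84 | d = 180 | Difference |
|---|---|---|---|
| 6 months | 44.2 days | 100.2 days | 56.0 |
| 12 months | 43.1 days | 95.1 days | 52.0 |
| 18.3 months | 42.7 days | 93.4 days | 50.7 |

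Spread over a cohort of 30, the smallest combination is 50.7 × 1.5/30 ≈ 2.5 days and the largest is 56.0 × 4.5/30 ≈ 8.4 days. This is an illustration and not an estimate of bias. It supposes that progression is ascertained at each contact and dated to that contact, neither of which the plan says.

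**Step 4. Cohort 2 primary endpoint**

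The design figure comes first. The trial continues if at least 1 of 15 respond and succeeds if at least 4 of 25 do:

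P(success) = Σ over x = 1 to 15 of C(15,x) p^x (1−p)^(15−x) × P(Bin(10,p) ≥ 4 − x).

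At p = 0.25 this gives 0.9008, which agrees with the stated 90%. At p = 0.05 it gives 0.0336, which is within the stated 0.05 read as a ceiling.

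Now let w be the share of responders who lose confirmation, and replace p by p(1 − w). The values of w are assumptions.

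| w | Power at 25% | Significance level at 5% |
|---|---|---|
| 0 | 90.1% | 0.034 |
| 5% | 87.5% | 0.029 |
| 10% | 84.3% | 0.024 |
| 15% | 80.5% | 0.020 |
| 20% | 76.2% | 0.016 |
| 30% | 65.5% | 0.010 |

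Both columns fall as w rises, so the error is conservative.

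The plausible w is small. At 25% response, 25 patients give 0.25 × 25 = 6.25 responders. If 5% to 15% of them refuse at any time, independently of response, that is 0.31 to 0.94 patients. Only those who refuse between the first response and the repeat scan are affected. Under that assumption 5% to 15% is an upper bound for w.

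**The case against.** The strongest reply is that little is actually lost.

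- **Events are still collected.** The status form covers disease status as well as survival and is due at PD and at death. A reader might infer that PFS in refusers is not measured at all. The documents do not support that: reported progression and deaths are captured, and what is missing is scheduled imaging.
- **Confirmation is still required.** Section 11.33 has no off-treatment exemption, and Section 18.1 lists a RECIST form at end of treatment. A reader might infer that the plan waives the repeat scan for refusers. It does not. What stands is that the scan has no visit or form once the patient is in event monitoring. An end-of-treatment scan may also fall less than 4 weeks after the first response.
- **A withdrawal scan may exist.** The column headings of the Section 4.0 test schedule are missing from the text reviewed, so a tumour measurement at withdrawal cannot be ruled out. One such scan would not replace assessment until PD.
- **Section 13.4 asks for 12-weekly observation until PD after treatment is discontinued.** In context this concerns patients who finish the treatment period, and it does not override Section 13.2.
- **The direction of bias is unproven.** It is tempting to say that late detection lengthens PFS. With no censoring rule, these patients might instead be censored at their last scan, and the direction is then unknown. PFS is also estimated within each cohort, with no comparator or decision rule.
- **Patients who choose other therapy are a different case.** Section 13.3 moves them to event monitoring too, and a scan after a new therapy cannot be credited cleanly to study treatment. The point does not extend to them.

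These replies narrow the point but leave the difference in imaging between Sections 13.2 and 13.3 unexplained.

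**Conclusion.** The point holds for patients who refuse further treatment without PD and have not started other therapy. For them, whether progression is looked for by scan depends on the recorded reason for stopping, and Sections 13.2 and 18.1 do not agree on what is collected while they remain free of PD.

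The number affected is probably small: 1.5 to 4.5 per cohort if 5% to 15% stop this way, a range that is assumed. The size and direction of the effect on PFS cannot be determined from the documents.

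For the Cohort 2 primary endpoint, any loss is of power only and not of false-positive control. Under the same assumed range, and with refusal independent of response, power stays between 80.5% and 90.1%, and probably near the upper end. A reader might carry this over to the Cohort 1 primary endpoint, but Section 16.12 does not make confirmation part of that definition.

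This is a cheap improvement and does not put the design in doubt.

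**What to change.** Limit Section 13.2 to patients with PD and patients who start alternative anticancer therapy.

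Amend Section 13.3 so that patients who stop protocol treatment without PD for any other reason, including refusal of further treatment, enter the existing Observation schedule. Tumour assessment there continues every 84 days until PD, start of other anticancer therapy, or withdrawal of consent to clinical follow-up. If a first CR or PR is awaiting confirmation, name the Section 11.33 repeat scan as part of that schedule.

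This is a wording change in two paragraphs. The Observation phase already carries the RECIST and Supporting Documentation forms, so no new form is needed, and sample size and decision rules are unchanged. The cost is additional 12-weekly scans for a few consenting patients per cohort (1.5 to 4.5 under the assumed refusal range). A one-line PFS censoring rule in Section 16.32 would usefully accompany it.
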